In addition to evaluating the effects of NAC, the proposed Phase II proof-of-concept study is designed to gather key data to inform future Phase III treatment efficacy trials for adolescent AUD, including effect size estimates. There is no currently established template for adolescent AUD pharmacotherapy trials. While adult trials may be informative, adolescents with AUD often differ from adults in alcohol use patterns, use-associated problems, and receptiveness to, as well as adherence with, treatment. Before proceeding to a Phase III efficacy trial in adolescents, a number of developmentally-informed methods must be embedded and evaluated for feasibility and value in a proof-of-concept trial. In addition to traditional, established, office-based clinical trial procedures, we propose utilizing mobile technology to improve data collection, engagement, and medication adherence. We additionally propose comparing the value of a cross-section of self-report and biological measures of alcohol use and related behaviors, to determine the most appropriate measures for inclusion as efficacy outcomes in Phase III trials.

With these methodological considerations in mind, and in response to National Institute on Alcohol Abuse and Alcoholism (NIAAA) RFA-AA-18-009 *Medications Development for the Treatment of Alcohol Use Disorder*, we propose preliminarily testing the effects of NAC, compared to placebo, on a platform of weekly evidence-based brief alcohol intervention for adolescents with AUD (*N*=120). We will (1) conduct an 8-week, intent-to-treat, double-blind, parallel-group, randomized, placebo-controlled trial of NAC (2400 mg per day); (2) examine standardized, repeated dependent measures of clinical outcomes at baseline, throughout treatment, and at post-treatment follow-up; and (3) employ mobile technology to improve data collection, engagement, and medication adherence. The following specific aims are proposed:

Specific Aim 1. To evaluate the effect of NAC, as compared to placebo, in reducing alcohol use (total standard drinks) among treatment-seeking adolescents with AUD.

Specific Aim 2. To evaluate the feasibility and utility of implementing developmentally-informed methods, including those that leverage mobile technology, to conduct a randomized, placebo-controlled trial of a pharmacotherapy for adolescent AUD.

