Specific Aim 2a: Examine agreement between self-report (mobile technology-delivered daily self-report, Timeline Follow-Back) and biomarkers (ethyl glucuronide, carbohydrate deficient transferrin, phosphatidylethanol, alcohol breathalyzer) of alcohol use.

Version: 16; Version Date: 11JULY2023

Specific Aim 2b: Examine agreement between measures of medication adherence (mobile technologydelivered video of medication taking, Medication Event Monitoring System, pill count, self-report).

Adolescence is a critical developmental stage involving marked elevation in alcohol initiation, progression to AUD, and development of significant, lasting adverse outcomes from use. Effective treatments must be developed for AUD in this especially vulnerable age range. The identification of a well-tolerated, effective pharmacological treatment would represent a significant advance and could yield tremendous public health impact. The proposed trial will provide critical data to evaluate NAC as a highly promising pharmacotherapy for adolescent AUD, and regardless of NAC versus placebo outcomes will provide key methodological guidance for future randomized controlled trials of pharmacotherapies for adolescent AUD.

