5.0 Inclusion and Exclusion Criteria/ Study Population

Inclusion Criteria

Participants must be age 13 to 25, must be able to understand the study and provide written informed consent (for those under age 18, parent/legal guardian must be able to provide consent and participant must be able to provide assent), must be a current moderate or heavy drinker by established adolescent criteria (see figure),⁴⁹ must meet

criteria for current AUD and express interest in AUD treatment, and (individuals assigned female at birth) must agree to use appropriate birth control methods during study participation: oral contraceptives, contraceptive patch, barrier (diaphragm or condom), levonorgestrel implant, medroxyprogesterone acetate, complete abstinence from sexual intercourse, or hormonal contraceptive vaginal ring. Participants must also have successfully completed the YC Intake Protocol (PRO#94743) within approximately 30 days of formal study screening.

Exclusion Criteria

Participants must not score >10 on the Clinical Institute Withdrawal Assessment for Alcohol,⁵⁰ as this would warrant more acute medical intervention than offered in the trial. Participants must not have known allergy or intolerance to NAC, no current use of *N*-acetylcysteine or any supplement containing *N*-acetylcysteine (must agree not to take any such supplement throughout study participation), individuals who are pregnant, lactating, or contemplating pregnancy/lactating over the next 6 months, must not be currently enrolled in ongoing treatment for AUD, and any other medical or psychiatric condition or other significant concern that in the Investigator's opinion would impact participant safety or compliance with study instructions, or potentially confound the interpretation of findings.

Co-Occurring Disorders

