
Version: 16; Version Date: 11JULY2023

corresponding 50% decrease in drinks per drinking day in the NAC treated group as compared to a 20% decrease in the placebo treated group [2.8 (SD=2.0) vs. 4.4 (2.0) drinks per drinking day].

Primary Data Analysis

Baseline clinical and demographic characteristics will be collected and contrasts of baseline characteristics and clinical predictors of substance use will be performed between groups. Continuous and ordinal characteristics will be compared using a Wilcoxon Rank-Sum test statistic while categorical characteristics will be compared using a Pearson Chi-Square test statistic. If a baseline characteristic is significantly associated with the outcomes of interest, the corresponding variables will be used as initial covariates in the model analyses. Secondarily, possible covariates will be tested for confounding effects on the models specified and when present, they will be included in the final adjusted model. Specific Aim 1: The primary measure of interest will be the estimated reduction in self-reported standard alcohol drinks and the associated variance around these estimates during the final four weeks of study treatment (weeks 5-8) in those randomized to NAC as compared to those randomized to placebo. The main effect of NAC versus placebo on the total number of standard drinks will be assessed using generalized linear models and modelbased means with associated standard errors will be reported. Analytic models will be computed both unadjusted and adjusted for significant covariates and confounders found in the preliminary analysis. Specific Aim 2: Self-reported drinking (weekly TLFB and mobile technology-delivered daily diary) as well as biomarkers of recent alcohol use (EtG, CDT, PEth, and alcohol breathalyzer) will be collected at study visits. Agreement between collection measures will be measured as percent agreement and kappa coefficients. Agreement will be assessed weekly during the entire time course of the treatment study and deviations between self-reported moderate/heavy use and biomarker-indicated moderate/heavy use will be assessed to characterize the reporting (under-reporting) of self-reported use amounts. Similarly, medication adherence will be measured at weekly study visits using self-report (self-report and mobile technology delivered video) and MEMS. Concordance percentages and kappa coefficients will be calculated between the adherence measurement methods. Due to high prevalence of self-reported adherence in substance use disorder studies, kappa coefficients will be calculated as the prevalence adjusted bias adjusted kappa (PABAK).⁶² Clustered logistic regression model using the methods of generalized estimating equations will be applied to assess the differences in self-reported drinking and medication adherence measurement methods on binary adherence outcomes over time.⁶³ Working correlation structures will be independently compared and the final model structures will be chosen using the quasilikelihood under the independence model criterion statistic.⁶⁴ The main effects of measurement method and visit, as well as the interaction between method and visit, will examined for significance.

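### Aim 2a promises to describe under-reporting of drinking amounts, but every method named for it is categorical or binary, so it can give no amount and its results shift with the cut-off

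*Combined protocol and SAP*

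**What the plan says.** Aim 2a (Section 1.0) is to "Examine agreement between self-report (mobile technology-delivered daily self-report, Timeline Follow-Back) and biomarkers", the markers being urine EtG, CDT, PEth and breathalyzer. The same section gives the purpose of comparing measures: "to determine the most appropriate measures for inclusion as efficacy outcomes in Phase III trials".

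Section 12.0, Primary Data Analysis, Specific Aim 2, names these methods:

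- "Agreement between collection measures will be measured as percent agreement and kappa coefficients".
- Weekly during treatment, "deviations between self-reported moderate/heavy use and biomarker-indicated moderate/heavy use will be assessed", in order to "characterize the reporting (under-reporting) of self-reported use amounts". No statistic is named for these deviations.
- A clustered logistic GEE to "assess the differences in self-reported drinking and medication adherence measurement methods on binary adherence outcomes over time", with method, visit and their interaction.
- A prevalence-adjusted, bias-adjusted kappa (PABAK), introduced with an adherence rationale: "Due to high prevalence of self-reported adherence in substance use disorder studies, kappa coefficients will be calculated as the prevalence adjusted bias adjusted kappa".

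For Aim 2a the section names no correlation, regression on marker level, paired difference, limits of agreement or ROC analysis. Its text gives no biomarker cut-offs. The self-report criteria for moderate or heavy drinking are in a Section 5.0 figure that was not available for this review, so they cannot be called missing.

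Some of the data are quantitative. Self-report is in standard drinks (Section 10.0, Clinical Assessments), and the Study Timetable lists CDT as a percentage. The reporting scale for PEth is not stated. EtG is qualitative at remote visits (Section 11.0).

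**The concern.** The goal is about amounts and the methods are about categories. A participant who reports half of what he drinks but stays on the same side of the cut-off counts as full agreement. A smaller under-report that crosses the cut-off counts as disagreement. Percent agreement and kappa therefore mix the size of misreporting with the share of people who lie near the cut-off.

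Two things are at stake. The under-reporting result, as worded, could not be produced from the named statistics. And a choice of Phase III measures that leaned on kappa would partly reflect where each cut-off was placed. The size of under-reporting also matters beyond Aim 2, because the Aim 1 endpoint is itself self-reported drinks.

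**Working it through.** **What can be reproduced.** The plan gives no sample size, precision or target kappa for Aim 2a. Its only sizing is for Aim 1. With a difference of 15 drinks, SD 25, two-sided 5% and 80% power, I get 44 per arm (46 with the unrounded difference of 14.7) against the stated 45, and 45/0.75 = 60 per arm. That sizing is consistent and does not bear on this point. What follows is illustration under stated assumptions.

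**Check 1: one fixed under-report, several cut-offs.**

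Inputs: baseline drinks per 4 weeks with mean 49 and SD 26 (Section 12.0, Power and Sample Size). Assumed: a lognormal shape, a marker that classifies true drinks T without error, everyone reporting 0.7T, and the same cut-off c on both sides. The cut-off of 24 echoes the heavier-drinker threshold in Section 12.0 and 49 is the mean; 10 and 80 are chosen to span the range.

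- Log variance = ln(1 + (26/49)²) = 0.248, so log SD = 0.498. Log mean = ln 49 − 0.248/2 = 3.768.
- Marker-positive rate: p = P(T > c). Self-report-positive rate: q = P(T > c/0.7).
- Self-report positives are a subset of marker positives, so agreement Po = 1 − (p − q).
- Chance agreement Pe = pq + (1 − p)(1 − q). Kappa = (Po − Pe)/(1 − Pe). PABAK = 2Po − 1.

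Worked case, c = 49: p = 1 − Φ((3.892 − 3.768)/0.498) = 0.402. c/0.7 = 70, so q = 1 − Φ((4.248 − 3.768)/0.498) = 0.167. Po = 0.766, Pe = 0.565, kappa = 0.46.

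| Cut-off (drinks) | Marker + | Self-report + | Agreement | Kappa | PABAK |
|---|---|---|---|---|---|
| 10 | 99.8% | 98.7% | 99% | 0.22 | 0.98 |
| 24 | 88% | 68% | 80% | 0.44 | 0.60 |
| 49 | 40% | 17% | 77% | 0.46 | 0.53 |
| 80 | 11% | 3% | 92% | 0.35 | 0.83 |

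The under-report is 30% in every row. Changing its size does not restore an ordering: with a 50% under-report, agreement at a cut-off of 10 is still 94%, higher than the 77% that a 30% under-report gives at 49. PABAK is a rescaling of percent agreement, so applying it to drinking would not remove the dependence on the cut-off.

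**Check 2: can the order of two markers change?**

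Assume bivariate-normal self-report and marker with self-report positive in 50%. With p11 the probability that both are positive, and p and q now the two positivity rates, Po = 1 − p − q + 2·p11. Pe is 0.5 whenever one rate is 50%, so kappa = 2Po − 1.

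- Both markers cut at 50% positive, where p11 = 1/4 + arcsin(r)/2π. For r = 0.8, Po = 0.795 and kappa = 0.59. For r = 0.6, Po = 0.705 and kappa = 0.41.
- The r = 0.8 marker cut at 15% positive: Po = 0.640 and kappa = 0.28, now below the weaker marker at 50%.

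The highest kappa possible with rates of 50% and 15% is ((1 − 0.35) − 0.5)/0.5 = 0.30, so most of the fall comes from the mismatch in positivity. Showing positivity rates beside kappa makes that visible.

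**The case against.** Several counter-arguments have force.

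- A reader might infer that percent agreement and kappa are the only statistics. They are not: the plan also has the deviations in moderate/heavy use and the GEE. The deviations can show the direction and frequency of misreporting by category. They are still categorical, and the GEE outcome is binary, so neither supplies an amount.
- A reader might infer that quantitative data are discarded, or that everything is forced into a 2×2 table. The text does not say so. Drinks are analysed quantitatively in Aim 1 and in the secondary count models, kappa also works with more than two categories, and the number of categories is not known here. The fair statement is that no quantitative method is named for Aim 2a.
- A reader might infer that markers will be ranked by kappa. No such rule is written. Section 1.0 states only the purpose.
- Eligibility ("must be a current moderate or heavy drinker by established adolescent criteria") might suggest lopsided categories throughout. It describes entry, whereas agreement is assessed during treatment, when Section 12.0 assumes drinks fall by 20% to 50%. Lopsidedness alone also does little: at correlation 0.7, kappa is 0.49 with both measures 50% positive and 0.44 with both 85% positive. Large falls need mismatched rates, and when agreement is the question, such a mismatch is real disagreement.
- A quantitative analysis does not automatically deliver amounts. Rank correlation is unchanged if everyone halves their reported drinks. Regression on marker level within this sample has no external calibration to say what level a true amount should give. This stands, and it limits the remedy.
- Scope is narrow. Blood is drawn only at screening and weeks 4, 8 and 26 (the last column also serving early termination), and never at remote visits. Alcohol outcomes other than the primary are exploratory.

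None of this closes the gap between a goal stated in amounts and methods that are all categorical.

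**Conclusion.** The point holds in this form: Aim 2a states a goal about under-reported amounts, and the plan names only categorical or binary methods for it. Under the assumptions of Check 1, one uniform 30% under-report yields agreement from 77% to 99% and kappa from 0.22 to 0.46 on cut-off placement alone. The exact figures depend on the assumed lognormal shape, the error-free marker and the chosen cut-offs. The structural conclusion does not: category agreement cannot be turned back into drinks. Specifying the cut-offs would make the results reproducible but would not produce amounts.

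The consequence is confined to Aim 2a and to the Phase III guidance drawn from it. Aim 1, safety and data collection are unaffected. It is a worthwhile, inexpensive improvement and not a flaw in the trial's main result.

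**What to change.** Keep percent agreement and kappa, and print the self-report and marker positivity rates beside each kappa. Kappa stays the main statistic for breathalyzer and qualitative EtG. Add a prespecified quantitative analysis:

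1. **%CDT, and PEth where reported as a level**, at in-person visits with a blood draw (screening, weeks 4, 8 and 26). Give the rank correlation with drinks in the preceding weeks, over a window fixed in advance, and a regression of the (log) level on those drinks with clustering by participant. Describe the results as strength of tracking and as discordance relative to this sample, not as drinks under-reported.
2. **Diary against TLFB.** Give the mean paired difference in drinks with limits of agreement, using only days recorded independently by both. This restriction is needed because TLFB also fills in missing diary days (Section 10.0, Clinical Assessments) and the Study Timetable has it confirming the daily reports. This comparison is between two self-reports and does not replace the biomarker comparison.
3. **Wording.** Restate the biomarker goal as under-reporting of use category plus discordance with marker level.

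The cost is SAP wording and modest extra analysis, with no new visits, samples or participants. The downside is that no single statistic will then be common to all measures.

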12.0 Data Management

Statistical Methods

Power and Sample Size

This Phase II proof-of-concept trial is powered on the primary hypothesis that there will be a clinically significant differential in the decrease in total standard alcohol drinks and drinks per drinking day during the final four weeks of treatment (weeks 5-8) in the NAC group compared to the placebo group. In the proposed study, the two treatment arms, NAC and placebo, will be assessed for differences in drinking behavior using general linear models. In a prior pilot trial assessing adolescent drinking behavior (N=11), our team noted an average total of 49 (SD=26) drinks with 5.5 (2.0) drinks per drinking day during the 4 weeks prior to study enrollment. Additionally, although the participants noted in our prior CUD trial were not required to exhibit AUD nor was treatment targeted at drinking behavior, the heavier drinkers in the study (upper quartile of total drinks prior to baseline, ≥ 24 drinks/30 days) reported a mean of 58 (SD=30; median=54 drinks) drinks during the 4 weeks prior to study entry.²⁶ In this sample of heavier drinkers, those randomized to placebo had a median 10.7% decrease in total drinks at the end of CUD treatment (last 4 weeks of study treatment) as compared to a median 33.0% decrease in total drinks in the NAC treated group. Assuming a more robust treatment effect when alcohol use is the therapeutic target, a 50% decrease in total drinks during the final 4 weeks of study treatment in the active treatment group, as compared to baseline, would be a clinically relevant treatment effect. We conservatively estimate a similarly more robust 20% decrease in total drinks in the placebo treated group. Assuming similar baseline drinking behavior to the adolescent study (baseline mean=49 drinks/4 weeks) and a similar group level variance estimate as in the baseline study data (SD=25), we will have 80% power with a 5% type I error rate to detect the clinically relevant difference between a 50% decrease in the NAC treated group and 20% decrease in the placebo treated group (equivalent to 25 total drinks versus 40 total drinks during the final 4 weeks of treatment) with 45 participants randomized to each treatment group (n=90 total). Additionally, we anticipate that retention may be a challenge in this population, and we anticipate a 25% drop-out rate during study treatment, inflating the necessary randomized sample size to n=60 participants per treatment arm (N=120total randomized participants). The noted sample will have greater than 90% power to find a

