
All randomized participants will be included in the primary analysis (intent-to-treat; ITT) and all statistical models will be implemented using SAS v. 9.4.

Secondary Data Analysis

In addition to the primary use outcome, secondary models will assess overall alcohol abstinence, the proportion of drinking days and the proportion of heavy drinking days noted during the final 4 weeks of study treatment. The temporal pattern in weekly drinking behavior over the course of the entire study is also of interest. Weekly drinking data in this population is likely to follow a Poisson distribution and will be assessed using random effects Poisson/Negative Binomial models and in the case of a high number of participants achieving abstinence from weekly alcohol use, zero inflated models will be explored. Similarly, binary weekly abstinence data will be assessed using mixed effects logistic regression models to assess the log-odds of weekly abstinence in the NAC- versus-placebo treated participants. Durability of treatment effects will be assessed through analysis of post-treatment alcohol use data at the Week 12 and Week 26 post-treatment visits, using model development processes similar to Specific Aim 1.

To assess the association between alcohol use reduction and changes in functional outcomes (alcoholrelated problems; alcohol craving; cognitive task performance; anxiety, mood, and sleep quality measures; quality of life), general linear regression models will be developed. Outcome specific distributions will be used to model functional and cognitive outcomes (e.g., count, binary and Gaussian). For Gaussian distribution assumptions, residual normality will be assessed using QQ plots, and when deviations from normality occur appropriate transformations will be made.

Missing Data and Attrition

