Missing data are common in longitudinal alcohol clinical trials where use rates are the primary end point. The primary cause attributed to such missing data is participant attrition. Attrition can introduce bias into the parameter estimate and reduce study power, estimate precision and generalizability. In order to minimize missing data and study attrition, study simplification and enhanced communication between study coordinators and participants will be emphasized. We will make every effort to prevent attrition, e.g., phone/text/email reminders prior to visits, compensation for participation, meeting with participants in community if needed, and reinforcing adherence at each visit. However, these methods do not ensure that all data will be collected and appropriate analysis methods will be employed to accommodate missing data. Simply replacing missing data with the last observation carried forward or using worst case scenario adds substantial bias to both parameter and variance estimates.65,66 Maximum likelihood methods (ML) yield valid inferences assuming ignorable attrition (i.e., attrition is accounted for by covariates or the dependent variable measured prior to dropout). Additionally, Full Information Maximum Likelihood methods (FIML) will be implemented and compared to the results from the ML estimation to assess bias that may be present due to missing data.⁶⁷ In addition, in keeping with the Intent to Treat Principle, we will make every effort to continue assessments for the entire course of randomized treatment, even among those who fail to adhere to randomized assignment or stop participating in the study assigned intervention.

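### The Aim 1 model names no on-treatment drinking before week 5, so dropout linked to that drinking can bias the NAC effect if it differs between arms

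*Combined protocol and SAP*

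**What the plan says.** All of these places are in section 12.0 of the combined protocol and SAP unless noted.

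- **Primary Data Analysis, Aim 1.** "The main effect of NAC versus placebo on the total number of standard drinks will be assessed using generalized linear models". The outcome window is weeks 5-8. Models are run unadjusted and adjusted for baseline characteristics and confounders, and neither version is named as primary. Section 10.0 (Clinical Assessments) sets the same window against the four weeks before intake.
- **Analysis set.** "All randomized participants will be included in the primary analysis (intent-to-treat; ITT"). No mechanism is given for a person without a weeks 5-8 total.
- **Secondary Data Analysis.** Random-effects models of weekly drinking are planned, but only as secondary.
- **Missing Data and Attrition.** ML methods "yield valid inferences assuming ignorable attrition (i.e., attrition is accounted for by covariates or the dependent variable measured prior to dropout"). Full Information Maximum Likelihood (FIML) will be compared with ML, but its variables are not listed. Worst-case replacement is rejected as a source of substantial bias.
- **Power and Sample Size.** "we anticipate a 25% drop-out rate during study treatment".
- **Section 10.0, Retention Strategies.** The intent-to-treat analysis is described as treating participants as drinking at any visit they miss.

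**The concern.** The plan justifies its handling of dropout by a condition that its primary model, as described, can meet only in part. The outcome measured before dropout is drinking in weeks 1-4. In a model with one weeks 5-8 total per person and baseline-type covariates, that information has no place. ML then amounts to an analysis of the observed totals.

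Suppose participants who are still drinking heavily in weeks 1-4 leave one arm more than the other. The missing-data section would call this ignorable, yet for the Aim 1 model it is not. The NAC-placebo difference could be understated or overstated, although the daily reports and weekly visits already collect the data that would correct it. This is separate from any worry about dropout that depends on unobserved drinking.

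**Working it through.** **1. The plan's own figure.** Inputs from Power and Sample Size: "we will have 80% power with a 5% type I error rate"; "equivalent to 25 total drinks versus 40 total drinks during the final 4 weeks of treatment"; "a similar group level variance estimate as in the baseline study data (SD=25"); "with 45 participants randomized to each treatment group (n=90 total"). A two-sided test is assumed.

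- Normal approximation: n = 2 × (1.96 + 0.842)² × 25² / 15² = 43.6, so 44 per arm. The t-test solution is 44.6, so 45, with 80.4% power.
- Dropout: 45 / (1 − 0.25) = 60 per arm.

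The figure reproduces. It counts 15 of 60 per arm as supplying no outcome.

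**2. What the likelihood uses.** Let E be weeks 1-4 drinks, Y weeks 5-8 drinks, and x baseline covariates. The Aim 1 model contributes f(Y | arm, x). If Y is missing, this integrates to 1 and the person drops out of the likelihood. A joint model contributes f(E | arm, x) × f(Y | E, arm, x), so the person still contributes through E. FIML on one total per person is the same as ML.

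**3. Size of the bias.** Assumptions, not in the documents: correlations of 0.7 (early-late), 0.5 (baseline-early) and 0.4 (baseline-late); SD 25 throughout; logistic dropout with slope 1 per 25 early drinks; all dropout before week 5.

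Let Δ be the amount by which mean early drinking among those who stay falls below that of everyone randomized to the arm:

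Δ = −25 × E[z(1 − π(z))] / E[1 − π(z)], with π(z) = 1/(1 + exp(−c − z)), z standard normal, and c set to give the arm's dropout rate.

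This gives Δ = 4.3, 5.3 and 6.3 drinks at 20%, 25% and 30% dropout, and 0 where dropout is unrelated to early drinking. The bias is then

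- unadjusted: 0.7 × (Δ placebo − Δ NAC);
- baseline-adjusted: about (0.7 − 0.4 × 0.5) × (Δ placebo − Δ NAC) = 0.5 × (Δ placebo − Δ NAC).

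Positive values mean that the NAC effect is understated. The last column is a simulation with 1,000,000 per arm and a true difference of 15.

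| Dropout pattern | Δ placebo, Δ NAC | Formula: unadjusted / adjusted | Simulation: unadjusted / adjusted |
|---|---|---|---|
| Same slope, 25% in each arm | 5.3, 5.3 | 0 / 0 | 0.03 / 0.03 |
| Same slope, 30% placebo v 20% NAC | 6.3, 4.3 | 1.4 / 1.0 | 1.40 / 1.04 |
| Same slope, 20% v 30% | 4.3, 6.3 | −1.4 / −1.0 | −1.38 / −1.04 |
| Heavy early drinkers leave placebo only | 5.3, 0 | 3.7 / 2.7 | 3.73 / 2.70 |
| Heavy early drinkers leave NAC only | 0, 5.3 | −3.7 / −2.7 | −3.75 / −2.72 |

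Dropout on baseline drinking alone gave about 0. With correlations of 0.8, 0.6 and 0.5, the adjusted factor is again 0.8 − 0.5 × 0.6 = 0.5. The unadjusted simulation figures rise to 1.59 for 30% v 20% and 4.24 for placebo only. Bringing weeks 1-4 drinking into the likelihood left a bias within 0.1 drink in every case.

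**4. At the trial's size.** These are runs with 60 per arm, log-normal totals, early-late correlation 0.7 and 25% dropout in each arm.

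- Placebo only, true difference 15: estimates of 11.0 to 11.3 unadjusted and 12.2 to 12.8 adjusted. With a baseline correlation as high as 0.7, the adjusted estimate is 13.6. Rejection rates are 65% unadjusted and 79% to 93% adjusted.
- NAC only, true difference 15: 18.6 to 18.8 unadjusted, 16.3 to 17.7 adjusted.
- NAC only, no true effect: type I error 11% unadjusted, 7% to 9% adjusted.
- Predicting missing late totals from early drinking within arm: 14.8 to 15.4 with a true effect, and within 0.5 of zero without one.

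**The case against.** A reader might infer that ignorable dropout as such biases the Aim 1 estimate. The documents do not support that. The plan's condition also covers dropout explained by covariates, and that does no harm when those covariates are in the model. Dropout driven by early drinking does almost none when its slope and rate match across arms. Nothing in the documents says that dropout will differ by arm.

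Nor is weeks 1-4 drinking explicitly excluded. Its absence is inferred from silence in the Aim 1 text. The missing-data section's mention of the outcome before dropout may hint at repeated measures, and FIML is planned expressly to look for bias from missing data.

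The calculations are also on the severe side. The expected 25% loss is spread over eight weeks, so some leavers will have partial weeks 5-8 data. Timeline Follow-Back fills gaps in the daily reports, and assessment continues after a participant stops the intervention. Baseline adjustment removes roughly a third to two thirds of the bias.

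These points limit the size of the problem and the certainty of the wording. They do not close the gap. The weekly models are secondary, and FIML is a comparison without listed variables and is not said to replace the Aim 1 estimate. Pre-treatment drinking is not named as a covariate. Treating missed visits as drinking supplies no drink count and sits badly with the rejection of worst-case replacement. The collection measures reduce missing data but set no analysis for those lost.

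**Conclusion.** The point holds as a conditional one. As written, the plan does not say how drinking before dropout enters the primary estimate, so its appeal to ignorable attrition is unsupported for Aim 1. Bias can arise in either direction if dropout, or its link to early drinking, differs by arm.

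Against the planned 15 drinks, a plausible size is about 1 drink adjusted (1.5 unadjusted) for 30% v 20% dropout. It is about 2-3 drinks adjusted (4 unadjusted) if heavy early drinkers leave one arm only. In that pattern, confined to NAC and with no true effect, the type I error is about 7-9% adjusted and 11% unadjusted. All of this rests on assumed correlations and slopes, and on every dropout leaving before week 5.

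Larger figures can be produced, such as a type I error of 25-26% unadjusted. They need opposite dropout patterns in the two arms, which the documents give no reason to expect. The sample size is not in question.

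**What to change.** In Primary Data Analysis (Aim 1) and in Missing Data and Attrition, state that the primary estimate uses all observed weekly drink totals, by one of two named routes:

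- a likelihood model of weekly totals for weeks 1-8, with arm by week, pre-treatment drinks, school status and sex, testing the weeks 5-8 contrast; or
- multiple imputation by arm of missing weekly totals from pre-treatment drinks, the stratification factors and all observed weekly totals, using a method suited to skewed counts, followed by the planned weeks 5-8 model.

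Report the one-total model on observed data as supporting. Reconcile the missed-visit assumption under Retention Strategies with the rejection of worst-case replacement. Settle this before unblinding, so that no choice between differing ML and FIML results is made afterwards.

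The cost is a longer analysis description and some extra SAS programming. No new data are needed and N stays at 120.
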